3.10.9 Adverse Events

Adverse Events

All AEs recorded in the screening period will be reported as baseline signs and symptoms.

A summary table will be presented of the number (and percentage) per vaccination period both per subject and for the number of events for the following events:

- Any AEs;
- Any treatment emergent AEs (i.e. onset date within 28 days after vaccination); note all SAEs are automatically considered treatment emergent regardless of onset date-
- Any Causally Related AEs (i.e. missing, unknown, not evaluable, possibly, probably, or definitely related AE); note that all local solicited AEs are automatically considered causally related;
- Any Causally related Treatment Emergent AEs;
- Treatment Emergent Severe AEs (Grade 3 or higher, for grading please refer to the CTP);
- Severe Causally related treatment emergent AEs);
- Non-serious Treatment Emergent AEs;
- SAEs;
- AESIs;
- AEs leading to discontinuation of treatment

In addition, the incidence of AEs will be calculated (i.e. the number of subjects developing a treatment emergent AE divided by the number of subjects at the time of the vaccination) with corresponding 95% Clopper-Pearson CI. The incidence of any AE will also be calculated for each vaccination period, overall and per subject.

For analysis the information will be based on the data provided from Screening Visit up until FU Visit.

All AEs will be listed by subject, including demographic information, SOC and PT.

According to the CTP no new AEs should be reported during the FU phase, except SAEs and AESIs, but if any are reported then they will be listed but considered non-treatment emergent.

The number of subjects with at least one treatment emergent AE will be compared between the groups by means of Fisher's exact test.

Serious Adverse Events

The number of subjects with at least one SAE will be compared between the groups by means of Fisher's exact test.

SAEs will be listed in the same manner as AEs.

Adverse Events of Special Interest

AESIs will be reported separately but in the same way as SAEs.

Solicited Local AEs

Solicited local AEs will be summarized by PT after each vaccination, and broken down by maximum intensity.

In addition, the incidence will be calculated by severity (i.e. the number of subjects developing a particular local solicited AE during the 15-day period after each vaccination divided by the number of subjects at the time of the vaccination) with corresponding 95% Clopper-Pearson CI. The incidence will also be calculated for any solicited local AE for each vaccination period and per subject.

The duration of the AEs will be included in the listing. The duration of the AEs will also be summarized using the mean, SD, median, minimum and maximum.

Solicited General AEs

Solicited general AEs will be summarized in the same manner as solicited local AEs.

In addition a similar summary table will be produced for relationship of the AEs to trial vaccine. Also the incidences of causally related AEs, and those with casually related with Grade ≥ 3 will be summarized per vaccination period and overall by subject.

Unsolicited AEs

Treatment emergent unsolicited AEs will be summarized by SOC and PT and vaccination period and by subject.

A summary of the number of AEs by intensity and by relationship to trial vaccination will also be presented.

The number of AEs with a reasonable possibility of being related to the vaccine will be presented in a separate listing and summarized in a table by SOC and PT and vaccination and by subject.

Non-treatment emergent AEs will only be flagged and included in the listing, but will not be included in the tables.

Assessment of ACAM2000[®] Vaccination Site

The following additional four measurements will be derived from the subject's memory aids:

- maximum lesion diameter measured in mm
- maximum erythema measured in mm
- maximum induration measured in mm
- healing time (calculated using date scab fell off)

For descriptive purposes the median for each group (and overall for both groups) will be calculated along with non-parametric confidence intervals for the median (Hahn, 1991). This will be obtained using the SAS Univariate procedure with the option CIPCTLDF. In addition the minimum and maximum value will be displayed.

The medians in Group 1 and Group 2 will be presented along with the 95% non-parametric PB confidence interval of the ratio.

The investigators measurement of the lesion size, erythema and induration will be presented in a similar way for the Day 7, Day 14 and Day 28 post ACAM2000[®] vaccination.

In addition, a blinded ITRC will classify individual takes as either full, partial or absent. The details of how the ITRC makes the classification will be described in a separate ITRC Charter. Clopper-Pearson confidence intervals will be calculated for the proportions of subjects with either full, partial and absent takes as classified by the ITRC.

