An adverse event (AE) with onset either on the day of a vaccination, but after the vaccination, or within the 28 days following a vaccination.

Causally Related Adverse Event:

An AE with either a ‘possible’, ‘probable’, ‘definite’, ‘unknown’ or ‘not evaluable’ or missing relationship to the vaccine.

An adverse event with missing relationship and onset before the first vaccination will not be assumed to be causally related.

Adverse Drug Reaction:

A causally related treatment emergent AE.

Serious Adverse Event:

All Serious Adverse Events (SAE) recorded with onset after the first trial vaccination and before the end of the FU phase are considered as treatment emergent regardless of the day of onset.

Adverse Events of Special Interest:

Any Adverse Event of Special Interest (AESI) which is also classified as serious will be included in the analysis of SAEs and will not be included in the analysis of AESIs. All AESIs recorded with onset after the first trial vaccination and before the end of the FU phase are considered as treatment emergent regardless of the day of onset.

Assay Cut-off Value:

The Assay Cut-off value (ACV) for the vaccinia-specific ELISA can be found in SOP BN0002809: “Automated ELISA for Detection of Vaccinia Specific Antibodies in Human Sera”, and for the vaccinia-specific PRNT can be found in SOP BN0003536: “Human Plaque Reduction Neutralization Test Using Vaccinia Virus Western Reserve”.

The Geometric Mean Titer:

The Geometric Mean Titer (GMT) is calculated by taking the antilogarithm of the mean of the \log_{10} transformed titers. Antibody titers below the ACV will be given an arbitrary value of one for the purpose of this calculation.

Seronegative and Seropositive Result:

A seronegative result is a titer below the ACV, while a seropositive result is a titer equal to or above the ACV.

Seroconversion:

Seroconversion is defined at each post baseline visit as either the appearance of antibody titers \geq ACV for initially seronegative subjects or a doubling or more of the antibody titer compared to baseline titer at Visit 1 for initially seropositive subjects. Seroconversion is not calculated if either the Visit 1 or respective post baseline visit titers are missing.

Maximum Lesion Area:

The Maximum Lesion Area (MLA) is defined as the maximum of two measurements: the lesion area measured on Day 6-8 (after scarification) or the lesion area measured on Day 13-15 (after scarification).

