1.1 Trial Description

This is a randomized, open-label Phase III non-inferiority trial to compare indicators of efficacy for MVA-BN[®] smallpox vaccine to ACAM2000[®] in 18-42 year old healthy vaccinia-naïve subjects.

A total of 440 vaccinia-naive subjects will be assigned randomly to two parallel treatment groups in a 1:1 ratio, 220 subjects in Group 1 and 220 subjects in Group 2.

Group 1:

One 0.5 ml standard dose MVA-BN[®] liquid-frozen vaccine contains a nominal titer of 1×10^8 tissue culture infectious dose 50% (TCID₅₀) Modified Vaccinia Ankara – Bavarian Nordic (MVA-BN[®]).

Two vaccinations each of 0.5 ml MVA-BN[®] vaccine will be administered four weeks apart (Day 0 and Day 28) as a subcutaneous (s.c.) injection in the non-dominant upper arm, followed by a single vaccination of ACAM2000[®] administered four weeks after the second MVA-BN[®] vaccination (Day 56). As per the prescribing information: one dose of reconstituted ACAM2000[®] vaccine consists of $2.5\text{-}12.5 \times 10^5$ plaque forming units of live vaccinia virus. A droplet (~ 0.0025 ml) vaccine is picked up with a bifurcated needle and is administered by the percutaneous route (scarification) using 15 jabs of the bifurcated needle.

Group 2:

A single vaccination of ACAM2000[®] will be administered at Day 0.

The active phase of the trial will begin at Day 0 (Visit 1) and continue through the second MVA-BN[®] vaccination (Day 56) and until 28 days after the ACAM2000[®] vaccination of Group 1 subjects (Visit 10). The active phase of the trial will begin at Day 0 (Visit 1) and continue until 28 days after the ACAM2000[®] vaccination of Group 2 subjects (Visit 4).

A remote Follow-up (FU) Visit by telephone or email is planned six months after the last trial vaccination. Only if there is a medical need, will the subject be asked to come back to the site or at the FU Visit (and specifically in the case of deployed military subjects) at another medical unit as agreed upon by the Principle Investigator.

The total duration (including screening period) is up to 22 weeks for Group 1 and up to 18 weeks for Group 2, plus remote correspondence (e.g. a phone call or email) six months after the last vaccination. If the remote correspondence reveals a medical need or any underlying condition that requires further examinations, the subject will be called in for a physical visit.

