3.8.2 Assignment of AEs to Vaccination Period

Each AE will be assigned to a vaccination period using date and time of vaccination and date and time of start of AE. If not specified otherwise all AE tables will be presented divided into the following vaccination periods:

For Group 1:

- Vaccination Period 1 covers from Visit 1 (immediately after the first vaccination) until Visit 4 (just before the second vaccination).
- Vaccination Period 2 covers from Visit 4 (immediately after the second vaccination) until Visit 7 (just before the third vaccination).
- Vaccination Period 3 covers from Visit 7 (immediately after the third vaccination) until Visit 10.
- The Overall MVA-BN[®] Vaccination Period is the combination of Vaccination Periods 1 and 2.

For Group 2:

- Vaccination Period 1 covers from Visit 1 (immediately after the first vaccination) until Visit 4.

If start time is missing and start date of AE coincides with the date of a vaccination, the AE will be assigned to the vaccination period corresponding to the vaccination on this date.

Each AE starting at or after first vaccination not matching the definition of a solicited AE is defined as an unsolicited AE. If a solicited AE begins outside of the 15-day window following the last vaccination it will be considered an unsolicited AE regardless of the preferred term. If start time is missing and start date coincides with date of current vaccination, it will be regarded as a treatment emergent AE. If the start date is (partially) missing the AE will be regarded as a treatment emergent AE following the worst case principle. If the AE cannot be assigned to a vaccination period 1 or 2 because of a (partially) missing start date it will be assigned to the overall MVA-BN[®] vaccination period (Group 1). If the AE cannot be assigned to vaccination period 2 or 3 then it will not be assigned to a vaccination period. AEs which cannot be assigned

to a vaccination period will still be included in per subject based tables and in the listings (with partial dates).

AEs with onset after the active trial phase will be considered to fall within the FU phase.

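### The Fisher tests on subjects with any treatment-emergent AE or any SAE name no vaccination period, so they set three vaccinations in Group 1 against one in Group 2

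*SAP*

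**What the plan says.** SAP section 3.10.9 sets two between-group tests. "The number of subjects with at least one treatment emergent AE will be compared between the groups by means of" Fisher's exact test, and "The number of subjects with at least one SAE will be compared between the groups by means of" Fisher's exact test. AESIs are to be reported separately but in the manner of SAEs. No vaccination period is attached to any of these sentences.

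The SAP's General Definitions fix what is counted. A treatment-emergent AE starts on a vaccination day after the injection, "or within the 28 days following a vaccination". SAEs and AESIs count over a longer span: those "recorded with onset after the first trial vaccination and before the end of the FU phase are considered as treatment emergent", whatever the day of onset.

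SAP section 3.8.2 gives Group 1 three periods; "Vaccination Period 3 covers from Visit 7 (immediately after the third vaccination) until Visit 10". Group 2 has one; "Vaccination Period 1 covers from Visit 1 (immediately after the first vaccination) until Visit 4". Section 1.1 sets the end of follow-up: "A remote Follow-up (FU) Visit by telephone or email is planned six months after the last trial vaccination". The procedure schedules put that contact at weeks 34-38 in Group 1 and weeks 26-30 in Group 2.

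Two provisions point towards matched comparisons. Section 3.8.2 divides AE tables by vaccination period by default, and section 3.10.1 promises a presentation of the ACAM2000 phase between the groups. Neither is linked to the Fisher tests.

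**The concern.** The safety objective (SAP section 1.2.2) asks two things: how MVA-BN compares with ACAM2000 given alone, and how ACAM2000 after MVA-BN priming compares with ACAM2000 alone. A count of subjects with at least one event over all periods answers neither, because Group 1's count mixes MVA-BN and ACAM2000 reactions and has three opportunities to rise against one in Group 2.

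Two errors can follow. Equal risk per vaccination can give a small p-value for more AEs in the MVA-BN arm, produced only by the number of vaccinations. Conversely, a real reduction in reactions per vaccination can be cancelled by the extra windows. These are the only p-values that the SAP pre-specifies for AE and SAE incidence, so they are the ones likely to be quoted.

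**Working it through.** The documents give no power or error figure for these tests, so there is no stated figure to reproduce.

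**Inputs from the documents.** 220 subjects per group (SAP section 3.1); three windows against one (section 3.8.2 and General Definitions); last contact 182-210 days after the last vaccination, which falls on Day 56 in Group 1 and Day 0 in Group 2 (procedure schedules); 99% of vaccinia-naive ACAM2000 recipients with at least one AE (protocol section 2.3; 864 of 873 in the prescribing information, Table 3). The other risks are assumptions, shown over a range.

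**Treatment-emergent AEs.** Let each vaccination carry the same risk p in both groups, independently. The per-subject risk is p in Group 2 and q = 1 - (1 - p)^3 in Group 1. For p = 0.05, q = 1 - 0.95^3 = 0.143. The probability that the two-sided 5% Fisher test shows a significant Group 1 excess comes from exact enumeration over both binomials. The last column repeats it for one window per group.

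| p per vaccination | Group 1 | Group 2 | All periods: false Group 1 excess | Matched window: false Group 1 excess |
|---|---|---|---|---|
| 1% | 3.0% | 1.0% | 19% | 0.3% |
| 2% | 5.9% | 2.0% | 47% | 0.9% |
| 5% | 14.3% | 5.0% | 90% | 1.5% |
| 10% | 27.1% | 10.0% | 99.6% | 1.8% |
| 97% | about 100% | 97% | 65% | 1.2% |
| 99% | about 100% | 99% | 2.4% | 0.3% |

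Matched windows keep the one-direction error below 2.5%. At 99% nearly everyone in both groups has an event and the test can show nothing.

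**Dependence within subjects.** Suppose reactions follow a beta-binomial with correlation ρ, a = p(1 - ρ)/ρ and b = (1 - p)(1 - ρ)/ρ. Then q = 1 - b(b+1)(b+2)/[(a+b)(a+b+1)(a+b+2)]. For p = 0.05 and ρ = 0.4, a = 0.075, b = 1.425, and q = 1 - 11.84/13.125 = 9.8%. The false excess is then 43% at p = 5% and 73% at 10%. With ρ = 0.8 it is 6.7% and 12%. If the same subjects react every time, q = p and the excess vanishes.

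**Masking.** If each Group 1 window carries 5% and Group 2's ACAM2000 window 15%, the per-subject risks are 14.3% and 15%. The all-period test shows a significantly lower Group 1 in 3% of trials. A matched window (5% against 15%) does so in 93%.

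**SAEs.** Follow-up runs about 56 + 182 = 238 days against 182, a ratio of 1.31. For background SAEs at constant hazard, q = 1 - (1 - p)^1.31:

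| p in Group 2 | Group 1 | False Group 1 excess |
|---|---|---|
| 1% | 1.3% | 1.0% |
| 2% | 2.6% | 2.9% |
| 5% | 6.5% | 6.8% |

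The threefold factor would apply only to SAEs triggered by vaccination.

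**The case against.** The strongest defence is that the matched figures are largely planned already. Section 3.8.2 makes division by vaccination period the default for AE tables. Section 3.10.9 tabulates by period and uses subjects present at each vaccination as the incidence denominator. Section 3.10.1 adds the ACAM2000-phase comparison. One could read the Fisher tests as inheriting that division. That stands for the tables. It does not settle the tests, whose sentences name no period, and a programmer following them literally would pool all of them.

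It is also fair that the 5% row is a free assumption. The rates that the documents do give produce less: 2.4% at the 99% any-AE rate; about 6% if the 5.7 per 1000 rate of suspected myo-/pericarditis is put on all three windows (1.7% against 0.57%). The SAP does not say whether the tested count pools solicited with unsolicited events. If solicited events are included the test is probably near its ceiling, though at 97% the false excess is still 65%. If they are excluded, intermediate rates are plausible.

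Finally, protocol section 9.6 calls all tests of secondary endpoints descriptive, and a comparison of whole randomised regimens is legitimate if labelled as such. Both points stand, and they limit the severity.

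**Conclusion.** The point holds as a should-fix. The tests, read literally, compare unequal numbers of vaccinations and address neither safety contrast. For treatment-emergent AEs at assumed per-vaccination risks of 1% to 10%, a false Group 1 excess arises in about 19% to 99.6% of trials, given 220 per arm, equal risk at each vaccination and independence. Correlation within subjects lowers those figures, and near 99% the test is uninformative rather than biased.

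A reader might infer more: that equal risk is bound to appear as an excess in the MVA-BN arm, for SAEs as well as AEs, because the arms are observed for 12 weeks and 4 weeks. The documents do not support that. Those durations describe the active phase only. SAEs and AESIs are counted to weeks 34-38 and 26-30, and the resulting distortion for background SAEs is small (1.0% to 6.8% above). Nor is a confirmatory conclusion at risk, since both co-primary analyses are separate from these tests.

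**What to change.** In SAP section 3.10.9, tie each Fisher test to the periods of section 3.8.2, with subjects who received the vaccination opening the period as denominator. The main contrasts would be:

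- Group 1 Period 1 against Group 2 Period 1: MVA-BN against ACAM2000, both as randomised.
- Group 1 Period 3 against Group 2 Period 1: ACAM2000 with and without priming.

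Use the same windows for SAEs and AESIs, and report SAEs over full follow-up per person-time. Drop the all-period test, or label it as a comparison at unequal exposure. State whether the tested count includes solicited events.

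Two cautions belong in the text. The denominators for Periods 2 and 3 omit subjects withdrawn from further vaccination under protocol section 4.2.5, so those contrasts are no longer purely randomised. AESIs in Period 2 should not be tested against Group 2 Period 1: protocol section 8.2.7 schedules no troponin in Period 2 and an ECG only if clinically indicated, whereas Group 2 has both at Visit 3. Periods 1 and 3 do have both scheduled (Visits 3 and 9).

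The cost is SAP wording before database lock and re-use of existing period flags. No new data are needed. The downside is a few more descriptive contrasts that share a single Group 2 window and so are not independent of each other.

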3.8.3 General Considerations for AEs

MedDRA (Medical Dictionary for Regulatory Activities) version 18.0 will be used for coding of AEs.

Duration of an AE is calculated as follows:

Unsolicited AE: expressed in [days]

- end date of AE – start date of AE + 1
- in case of (partially) missing start date and/or (partially) missing end date imputed dates will be used in the calculation.
- in case the AE is ongoing at the end date, the duration will not be calculated

Solicited AEs: expressed in [days]

- end date of AE – start date of AE + 1 where end date is the last day the symptom is defined as an AE and start date is the first day symptom is defined as an AE (no matter if the AE occurred at every day between first day and last day).
- in case the AE is ongoing at the end date, the duration will not be calculated

Time interval between vaccination and start of AE are calculated as follows:

Relative day of start of AE is calculated as follows:

Unsolicited AEs: expressed in [days]

- start date of AE – date of vaccination of the corresponding period
- in case of (partially) missing start date no calculation will be done.

Solicited AEs: expressed in [days]

- start date of AE – date of vaccination of the corresponding period where start date is the first day a symptom is defined as an AE, and vaccination day corresponds to the day of vaccination for each period.

Local and General Unsolicited AEs

Any unsolicited AE which is recorded with the preferred term including the text “injection site” or “vaccination site” will be considered as a local reaction. Any other preferred terms which are

considered as local events will be documented in the DRM minutes. Any unsolicited AE not classified as a local AE will be classified as a General AE.

All available safety data collected during the FU phases will therefore be simply listed. However the new onset SAEs reported during the FU phase will be analyzed.

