In case any AESI is also an SAE it will be treated and reported as an SAE.

Prior and Concomitant medication

Assessment of ACAM2000[®] Vaccination Site

The following four measures will be derived from the subject's memory aids:

- healing time measured in days

- maximum lesion diameter measured in mm
- maximum erythema measured in mm
- maximum induration measured in mm

The following measurements will be made by the investigator at Day 0, Day 7, Day 14 and Day 28 visits following ACAM2000[®] vaccination

- lesion erythema measured in mm
- lesion induration measured in mm
- general appearance of the lesion

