3.10 Analysis and Presentation Methods

3.10.1 Listings and Descriptive Statistics

All individual data entered in the eCRF and derived data will be listed as measured in the Individual Subject Data Listing.

For ELISA and PRNT titers descriptive statistics will be based on Geometric Means and confidence intervals (CI). For other, continuous parameters, measurements will be summarized by means of descriptive statistics (i.e. number of observations (N), mean, SD, minimum (Min), median, maximum (Max)) and categorical data will be summarized by means of frequency tables (i.e. count and percentages) and CI, if not stated otherwise.

All tables and listings will be sorted by scheduled visit (and subject, if appropriate).

All tables will be presented split by treatment groups (Groups 1 and 2). A comparison of the ACAM2000[®] vaccination phase will also be presented between Groups 1 and 2.

Repeat assessments/measurements and unscheduled assessments/measurements will be included in the Individual Subject Data Listing. All other repeat values will be listed in a separate listing.

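### The AESI tables omit AESIs that are also serious, and the AESI test that the SAP implies compares regimens, not MVA-BN with ACAM2000

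*SAP*

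**What the plan says.** **Seriousness rule.** The AESI entry in the SAP's general definitions says that an AESI classified as serious "will be included in the analysis of SAEs and will not be included in the analysis of AESIs". SAP 3.9.2 repeats it: "In case any AESI is also an SAE it will be treated and reported as an SAE".

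**Analysis rule.** SAP 3.10.9 gives AESIs one sentence: "AESIs will be reported separately but in the same way as SAEs". The rule for SAEs just above it is: "The number of subjects with at least one SAE will be compared between the groups by means of Fisher's exact test". It names no vaccination period.

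**Time window.** The definitions say that "All AESIs recorded with onset after the first trial vaccination and before the end of the FU phase are considered as treatment emergent", whatever the day of onset. SAP 3.8.3 says of the follow-up phase: "All available safety data collected during the FU phases will therefore be simply listed", and then exempts only new SAEs.

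**Period displays.** SAP 3.8.2 splits adverse event tables by default into Group 1 Periods 1, 2 and 3, an overall MVA-BN period, and Group 2 Period 1. The overall MVA-BN "Vaccination Period is the combination of Vaccination Periods 1 and 2". The summary table in SAP 3.10.9 is per vaccination period and has rows for SAEs and AESIs, and Table 15.3.2.3 shows AESIs per vaccination period. The one between-group phase comparison named is in SAP 3.10.1, where the ACAM2000 "vaccination phase will also be presented between Groups 1 and 2".

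**Protocol.** Section 9.3.2 makes cardiac signs or symptoms indicating myo-/pericarditis a secondary safety endpoint, equates them with AESIs, and makes no exception for serious ones. Section 9.6 requires AESIs to be listed and tabulated separately and treats all secondary tests as descriptive. Section 3.2 asks for a safety comparison of MVA-BN and ACAM2000 given alone, as well as ACAM2000 after priming.

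**The concern.** Two things do not fit the protocol.

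First, the most serious cardiac events leave the table that is meant to report the cardiac endpoint. They are still reported, but among all SAEs. The reader gets two partial counts and no total.

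Second, if AESIs inherit the SAE test, the only between-group AESI result will set a three-dose regimen against a single dose. Both arms contain ACAM2000, so the contrast cannot answer the objective about the vaccines given alone. Group 1 is also looked at more often and for longer, so even two harmless vaccines would tend to show more AESIs in Group 1.

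At stake is how the cardiac safety of MVA-BN relative to ACAM2000 is presented. The co-primary endpoints are not affected.

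**Working it through.** The plan gives no AESI rate, power or interval to reproduce. The one related figure is the ACAM2000 label rate of suspected myo-/pericarditis in naive vaccinees (protocol Appendix IVc, 5.1.3): 5/873 = 5.73 per 1000, exact 95% CI 1.86 to 13.31, which agrees with the printed 5.7 (1.9 to 13.3).

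**1. The exclusion**

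- The endpoint in protocol 9.3.2 is all AESIs. The AESI tables hold all AESIs minus the serious ones.
- The total cannot be recovered by adding the AESI and SAE counts. SAEs include non-cardiac events, and one subject may have both a serious and a non-serious AESI.
- Nor does a single organ-class row give it. AESIs include symptoms, ECG findings and troponin rises (protocol 8.1.3.3). Protocol Table 1 files tachycardia, chest pain and raised troponin I under three different classes.
- Share affected: of the 10 cases in Appendix IVc, 5.1.3 (7 ACAM2000, 3 Dryvax), 2 were hospitalized, which meets a seriousness criterion. 2/10 = 20%, exact 95% CI 2.5% to 56%. Protocol 2.3 calls all 10 serious, which would be 100%.
- Expected number among 220 naive ACAM2000 recipients: 220 × 0.00573 = 1.26 cases, of which 0.25 would move at 20% and all 1.26 at 100%.

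**2. What a whole-group test would compare** (after first vaccination; schedules in protocol 1.5 and 8.2.7)

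| | Group 1 | Group 2 |
|---|---|---|
| Vaccinations | MVA-BN, MVA-BN, ACAM2000 | ACAM2000 |
| Scheduled ECGs | 2 (V3, V9) | 1 (V3) |
| Scheduled troponin I | 2 (V3, V9) | 1 (V3) |
| Cardiac questions | 6 (V3, V4, V6, V7, V9, V10) | 2 (V3, V4) |
| Days, active phase | (55-57) + (27-29) = 82-86 | 27-29 |
| Days, to end of follow-up | (55-57) + (182-210) = 237-267 | 182-210 |

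Period 1 is matched: in each group it is a first dose in randomized naive subjects, with 1 ECG, 1 troponin, 2 rounds of questions and 27-29 days. The overall MVA-BN period is not matched to Group 2 Period 1: two doses and about 56 days against one dose and about 28.

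**3. Illustration of the tilt**

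Assume no effect of either vaccine, 220 per group, background AESI probability b per period, and independent periods. Then Group 2 = b and Group 1 = 1 − (1 − b)^k. Take k = 2 if events surface only in the two periods with scheduled tests, and k = 3 if they surface in all three. The table gives the probability, by exact enumeration, that a two-sided 5% Fisher test is significant with Group 1 higher.

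| b | Whole group, k = 2 | Whole group, k = 3 | Period 1 against Period 1 |
|---|---|---|---|
| 0.5% | 0.9% | 4.5% | 0.03% |
| 1% | 5.2% | 19.2% | 0.3% |
| 3.0% (41/1371) | 24.0% | 67.8% | 1.2% |
| 4.5% (39/873) | 37.0% | 86.0% | 1.5% |

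The values of b are assumptions. The lower two lines borrow dyspnea rates from label Table 3 (Appendix IVc, 6.2.1) in previously vaccinated and naive ACAM2000 recipients. At b = 3%, Group 1 reads 5.9% (k = 2) or 8.7% (k = 3) against 3.0%. Relaxing the assumptions at b = 3%: a within-subject correlation of 0.4 (beta-binomial) lowers the probability to 10-25%, and a 4% follow-up AESI rate added to both groups lowers it to 14-44%.

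**4. Does the direction survive a real ACAM2000 effect?**

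Let ACAM2000 add r = 0.00573 in naive subjects, and let MVA-BN and primed ACAM2000 add nothing. Group 1 is lower only if (1 − b)^(k−1) > 1 − r. For k = 3 that is b < 1 − √(1 − r) = 0.29%, and for k = 2 it is b < r = 0.57%. Above those rates the whole-group contrast still points against MVA-BN.

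**5. Precision of the matched contrast**

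- At 3% in each group, the half-width is 1.96 × √(2 × 0.03 × 0.97/220) = 3.2 points.
- 0/220 has an exact upper 97.5% limit of 1.7%.
- Significance needs 6 against 0 events (p = 0.030). At 5.7 per 1000 against 0, the power is 0.2%.

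**The case against.** The other side has a good deal of the argument.

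- **A reader might infer that the plan offers no fair comparison of the two vaccines.** The documents do not support that. SAP 3.8.2, 3.10.9 and Table 15.3.2.3 put AESI counts side by side by group and period, including the matched Period 1 columns. A Clopper-Pearson interval for each AESI incidence arguably follows from SAP 3.10.9. What is missing is the designation of a contrast and an interval for the difference.
- **A reader might infer that serious cardiac events go unreported.** They do not. They appear in Table 15.3.2.1 by preferred term, in the SAE listings and in the SAE test, and protocol 9.6 has each SAE described individually. The rule also avoids double counting. Even so, the total for the named endpoint appears nowhere, and the period tables carry the same gap.
- **The test may not exist.** Reporting in the same way can mean layout only. Then no between-group AESI comparison is defined beyond the ACAM2000 phase, and the text still needs clarifying.
- **The test is descriptive, and its tilt runs against the sponsor's vaccine.** Both are true. No claim rests on it and it gives MVA-BN no false reassurance, but a misleading result in either direction is worth avoiding.
- **The 3% background is weak.** This stands. It is a diary-checklist symptom recorded after vaccination in another trial, not an AESI rate, and the 24-68% should not be read as a forecast.
- **A reader might fault the lack of a scheduled ECG or troponin after the second MVA-BN dose.** That is a consistent design choice. Questions continue at Visits 6 and 7, tests are available if clinically indicated, and the effect on counts cannot be determined from the documents.

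**Conclusion.** The concern holds in a limited form.

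The firmer part is the exclusion. It is written twice in the SAP, departs from the protocol's endpoint, and leaves no table with the total AESI incidence. For myo-/pericarditis alone the expected number moved is small: roughly 0.25 to 1.3 subjects per 220 naive ACAM2000 recipients, resting on ten earlier cases. Those few would be the most serious events.

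The second part rests on a literal reading of one sentence. On that reading, the whole-group test is a comparison of regimens under unequal observation. The imbalance follows directly from the schedules. Its size does not: the false-signal probability runs from about 1% to 86% across assumed backgrounds of 0.5% to 4.5%, with independent periods and no vaccine effect. The direction is against MVA-BN unless the background is very low.

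This is a matter of secondary safety presentation. It deserves correction because the correction is cheap.

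**What to change.** Change SAP 3.10.9, the AESI definition, SAP 3.9.2 and the table shells, in the final SAP version that is already foreseen before database lock:

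1. Count every AESI, serious or not, in Tables 15.3.2.2 and 15.3.2.3 and in the AESI row of the summary table, and keep serious ones in the SAE tables too. Add a note on the overlap.
2. Name Group 1 Period 1 against Group 2 Period 1 (FAS) as the MVA-BN against ACAM2000 comparison for AESIs. Give each incidence with a Clopper-Pearson interval and the difference with an exact 95% interval, read as an estimate.
3. Label any whole-group Fisher test as a comparison of regimens, and state whether follow-up AESIs enter it, since the definitions and SAP 3.8.3 disagree.

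**Cost:** SAP wording, one contrast and a note. No protocol amendment, visit, sample or assay is needed. **Downside:** serious AESIs appear in two tables, and the contrast covers only the first MVA-BN dose and has very low power for myo-/pericarditis.
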